11. APPENDICES

Appendix 1: Adverse Event Reporting

Adverse Events

Definition of Adverse Events

An adverse event (AE; or adverse experience) is defined as any untoward medical occurrence experienced by a patient or healthy adult subject, whether or not considered drug-related by the Investigator (or designee). A treatment-emergent adverse event (TEAE) is an AE that is reported after a dose of study drug.

The following are all AEs:

- unfavorable changes in general condition;
- subjective or objective signs/symptoms;
- concomitant diseases or accidents;
- clinically relevant adverse changes in laboratory parameters observed in a subject during a clinical study.

Adverse events comprise all disturbances of general health status, subjective and objective disease symptoms (including laboratory abnormalities that are deemed clinically significant by the Investigator or designee), and accidents observed in the context of a clinical trial, irrespective of a possible causal relationship with the administration of the trial substance.

Categorization of Adverse Events

The severity of AEs will be categorized based on the National Cancer Institute Common Terminology Criteria for Adverse Events (CTCAE) Version 5.0 as follows:

- **Grade 1 Mild:** Asymptomatic or mild symptoms; clinical or diagnostic observations only; intervention not indicated
- **Grade 2 Moderate:** Minimal, local, or noninvasive intervention indicated; limiting age-appropriate instrumental Activities of Daily Living (ADL)*
- **Grade 3 Severe or medically significant but not immediately life-threatening:** Hospitalization or prolongation of hospitalization indicated; disabling; limiting self-care ADL**
- Grade 4 Life-threatening consequences: An event that puts the subject at immediate risk of death
- **Grade 5** Death related to AE.

Note: Not all grades are appropriate for all AEs. Therefore, some AEs are listed within the CTCAE with fewer than 5 options for grade selection. Grade 5 (death) is not appropriate for some AEs and therefore is not an option. * Instrumental ADL refer to preparing meals, shopping for groceries or clothes, using the telephone, managing money, etc. **Self-care ADL refer to bathing, dressing and undressing, feeding self, using the toilet, taking medications, and not bedridden. The Investigator (or designee) will make a determination of the relationship of the AE to the study drug using a 2-category system according to the following guidelines:

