- **NOT RELATED** = The time course between the administration of investigational product and the occurrence or worsening of the AE rules out a causal relationship and another cause (eg, concomitant drugs, therapies, complications, comorbidities) is suspected
- **RELATED** = The time course between administration of investigational product and the occurrence or worsening of the AE is consistent with a causal relationship and no other cause (eg, concomitant drugs, therapies, complications, comorbidities) can be identified.

An AE is associated with the use of the drug if there is a reasonable possibility that the experience may have been caused by the drug.

Pregnancy

As information is available, a pregnancy (including pregnancy in female partners of male subjects) diagnosed through EOS or ET (if the subject discontinues from the study and does not complete a follow-up phone call) and for up to 90 days after study drug administration should be reported by the Investigator (or designee) via email to Covance or the Sponsor's Clinical Safety Representative within 24 hours of being notified. Covance or the Sponsor's Clinical Safety Representative will then forward the Pregnancy Form to the Investigator for completion.

email: [contact]

A subject becoming pregnant while on study drug will immediately be withdrawn from the study and ET study procedures will be performed. The subject or partner should be followed by the Investigator until completion of the pregnancy. If the pregnancy ends for any reason before the anticipated date, the Investigator should notify Covance or the Sponsor's Clinical Safety Representative. At the completion of the pregnancy, the Investigator will document the outcome of the pregnancy. If the outcome of the pregnancy meets the criteria for immediate classification as a serious adverse event (SAE; ie, postpartum complication, spontaneous abortion, stillbirth, neonatal death, or congenital anomaly), the Investigator should follow the procedures for reporting an SAE.

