Food and Drug Administration-reportable AEs are AEs that are associated with the use of the drug and represent events that are assessed as serious, related, and unexpected. Food and Drug Administration-reportable AEs will be reported by the CRU to the Sponsor and the responsible Institutional Review Board (IRB). Final determination of whether an event represents a suspected unexpected serious adverse reaction (SUSAR) will be the responsibility of the Sponsor.

Within 24 hours of when an AE that is potentially FDA-reportable is first recognized or reported, and within 24 hours of any SAE (regardless of whether the event is assessed as related or unrelated to study drug) being first recognized or reported, Covance or the Sponsor's Clinical Safety Representative will be notified by the Investigator or designee in writing using the following email address:

email: [contact]

To report the SAE, the completed report form should be sent by email to Covance or the Sponsor's Clinical Safety Representative within 24 hours of awareness. Incoming reports are reviewed during normal business hours. Additional reporting instructions and the SAE Report Form are provided in the Study Manual.

The IRB will be notified of any FDA-reportable AE within the timeframe required by the IRB. The IRB Serious and Unexpected Adverse Experience Submission Form will be completed and submitted with the copy of the written confirmation or summary of the AE.

| Clinical Chemistry Panel (Fasted): | Complete Blood Count (CBC): | Other Tests: |
|---|--|--|
| Alanine aminotransferase (ALT) Albumin Alkaline phosphatase (ALP) | Hematocrit Hemoglobin Mean corpuscular hemoglobin | Hemoglobin A1c (HbA1c) ^b Thyroid-stimulating hormone (TSH) ^b |
| Amylase | Mean corpuscular hemoglobin | Coagulation Parameters: |
| Aspartate aminotransferase (AST) Bilirubin (direct and total) Blood urea nitrogen Calcium Chloride Cholesterol Creatine kinase (CK) | concentration Mean corpuscular volume Platelet count Red blood cell (RBC) count RBC distribution width White blood cell (WBC) count WBC differential (percent and absolute): | Activated partial thrombin time Partial thromboplastin time Prothrombin time International normalized ratio Serology: ^b Human immunodeficiency virus (HIV) antibody |
| Creatinine Glucose Iron Lipase Magnesium | Basophils Eosinophils Lymphocytes Monocytes Neutrophils | Hepatitis B surface antigen (HBsAg) Hepatitis C virus (HCV) antibody |

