8.6. Safety and Tolerability Assessments

8.6.1. Adverse Events

All AEs will be coded using the Medical Dictionary for Regulatory Activities (MedDRA) Version 22.1. All AEs will be assigned severity grade using National Cancer Institute Common Terminology Criteria for Adverse Events (CTCAE) Version 5.0.

A treatment-emergent adverse event (TEAE) will be defined as an AE that starts during or after the first dose, or starts prior to the first dose and increases in severity after the first dose.

A treatment-related TEAE will be defined as a TEAE with a relationship of related to the study treatment (LOXO-305 or Omeprazole), as determined by the investigator.

The assignment of TEAEs to the associated treatments will be as follows:

- A TEAE occurring during or after Day 1 dosing and prior to Day 8 dosing will be assigned to '200 mg LOXO-305 (Fasted)' or '200 mg LOXO-305 (Fed)' depending on the subject's fasting status prior to Day 1 dosing.

- A TEAE occurring during or after Day 8 dosing and prior to Day 15 dosing will be assigned to '200 mg LOXO-305 (Fasted)' or '200 mg LOXO-305 (Fed)' depending on the subject's fasting status prior to Day 8 dosing.
- A TEAE occurring during or after Day 15 dosing and prior to Day 18 dosing will be assigned to '40 mg Omeprazole (Fasted)'.
- A TEAE occurring during or after Day 18 dosing will be assigned to '200 mg LOXO-305 + 40 mg Omeprazole (Fasted)'.

All AEs will be listed. In addition to the data recorded in the database, the listings will include derived onset time and duration. Onset time will be calculated from the time of the last dose for TEAEs only.

The frequency of subjects with TEAEs and the number of TEAEs will be summarized for the following categories:

- TEAEs (overall, serious, and leading to discontinuation) by treatment
- TEAEs by severity and treatment
- Treatment-related TEAEs (overall, serious, and leading to discontinuation) by treatment
- Treatment-related TEAEs by severity and treatment

The frequency of subjects will be summarized separately for TEAEs and treatment-related TEAEs by the following:

- System organ class, preferred term, and treatment
- Preferred term and treatment
- System organ class, preferred term, day of onset, and treatment

For the AE data the following rules will apply:

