- For the derivation of TEAE status: If the start date/time of an AE is incomplete or missing, an AE will be assumed to be a TEAE, unless the incomplete start date/time or the end date/time indicates an AE started prior to the first dose.
- For the derivation of treatment-related TEAE status: If the study treatment relationship for a TEAE is missing, a TEAE will be assumed to be a treatment-related TEAE.
- For the derivation of onset time: If the start date/time of an AE is missing, onset time will not be calculated. If the start date/time of an AE is incomplete, where possible, the minimum possible onset time will be calculated and presented in ' \geq DD:HH:MM' format (eg, if the date/time of the last dose is 01MAY2019/08:00 and recorded start date/time of an AE is 03MAY2019, then the minimum possible onset time will be calculated by assuming the AE started at the first hour and minute of 03MAY2019 [03MAY2019/00:00], thus will be presented as onset time \geq 01:16:00 in the listing).

- For the derivation of duration: If the end date/time of an AE is missing, duration will not be calculated. If the start or end date/time of an AE is incomplete, where possible, the maximum possible duration will be calculated and presented in ‘≤DD:HH:MM’ format (eg, if the start of an AE date/time is 01MAY2019/08:00 and its recorded end date/time is 03MAY2019, then the maximum possible duration will be calculated by assuming the AE ended at the last hour and minute of 03MAY2019 [03MAY2019/23:59], thus will be presented as duration ≤02:15:59 in the listing).
- For the calculation of summary statistics: If the severity of a TEAE is missing, a TEAE will be counted under the maximum severity possible, up to Grade 4 in the absence of a fatal outcome.
- For the calculation of summary statistics: If a subject experienced multiple TEAEs with the same preferred term for the same treatment, this will be counted as 1 TEAE for that treatment under the maximum severity recorded.

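### The two causality categories in Protocol Appendix 1 do not cover an event with compatible timing and an identifiable other cause, so the related classification can be inconsistent or too narrow

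*Protocol*

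**What the plan says.** Protocol Appendix 1 asks the Investigator to determine the "relationship of the AE to the study drug using a 2-category system according to the following guidelines". There is no third or unknown option.

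- **NOT RELATED** applies when the time course "rules out a causal relationship and another cause (eg, concomitant drugs, therapies, complications, comorbidities) is suspected".
- **RELATED** applies when the time course "is consistent with a causal relationship and no other cause (eg, concomitant drugs, therapies, complications, comorbidities) can be identified".

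The next sentence gives a different standard for a differently named concept: "An AE is associated with the use of the drug if there is a reasonable possibility" that the drug caused the experience. The Reporting part of the same appendix then describes FDA-reportable AEs as those that "are AEs that are associated with the use of the drug and represent events that are assessed as serious, related, and unexpected".

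The SAP adds no causality definition of its own. Section 8.6.1 defines a treatment-related TEAE as "a TEAE with a relationship of related to the study treatment (LOXO-305 or Omeprazole), as determined by the investigator". It also has a default for blanks: "If the study treatment relationship for a TEAE is missing, a TEAE will be assumed to be a treatment-related TEAE".

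**The concern.** A two-category scale works only if each definition is the complement of the other. Here each definition joins two conditions with 'and', and neither is the negation of the other. Some events therefore have no defined place. Two careful assessors could classify the same event differently and both comply with the protocol.

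The type of event left out is an ordinary one. Subjects are confined, dosed and sampled repeatedly, so many AEs will follow a LOXO-305 dose closely while a study procedure is a visible alternative explanation. Protocol 1.5 names blood collection and other procedures as sources of discomfort, and Protocol 7.2.1 already treats relation to study procedures as an attribution. A reaction at a sampling site some hours after a dose is one illustration.

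The classification is used in three places:

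- the treatment-related TEAE tables (SAP 8.6.1; Protocol 8.4 also presents AEs by relationship), which serve the secondary safety objective;
- the rule in Protocol 3.1 and 7.2.1 that, between EOT or ET and the follow-up call, non-serious AEs are reported only if assessed as related;
- the related element of FDA-reportable AEs in Appendix 1.

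In the second use, an event classed as not related is not reported, so later analysis cannot recover it.

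**Working it through.** No sample size or error rate is involved, and the plan gives no figure to reproduce. The check applies the two definitions to the possible cases.

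1. **Compatible timing, no other cause.** Both conditions for RELATED are met, so the event is RELATED.
2. **Timing excludes the drug, another cause suspected.** Both conditions for NOT RELATED are met, so the event is NOT RELATED.
3. **Compatible timing, another cause identifiable.** RELATED fails on its second condition because another cause can be identified. NOT RELATED fails on its first because timing does not exclude the drug. The event fits neither.
4. **Timing excludes the drug, no other cause suspected.** NOT RELATED fails on its second condition and RELATED on its first. This also fits neither, but with little practical effect, since an assessor would hardly call it related.

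One definition speaks of a suspected cause and the other of a cause that can be identified. Where a cause is only suspected and timing is compatible, the result depends on whether those terms are read as different. Case 3 does not depend on that reading.

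**Check against the reasonable-possibility sentence.** In case 3 the drug may still be a reasonable candidate: another identifiable cause does not exclude a contribution from the drug. Such an event can satisfy the sentence after the definitions, yet it cannot satisfy RELATED. If that sentence is a separate concept, it does not assign case 3 to a category. If it is the intended overall standard, the RELATED definition contradicts it. The text needs reconciling on either reading.

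**Check against the SAP default.** The missing-relationship rule acts only when the field is blank. In case 3 the Investigator will normally have entered something.

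**Reach of the post-treatment rule.**
- Length of the related-only window: 7 − 2 = 5 days to 7 + 2 = 9 days after EOT or ET.
- Its start for completers: last dose on Day 18, EOT on Day 25, so (25 − 18) × 24 = 168 hours after the last dose.
- Protocol 1.3.2 gives a half-life of about 18 hours, stated there as uncertain: 168 / 18 = 9.3 half-lives. With first-order elimination, 0.5^9.3 ≈ 0.002, or about 0.2% of drug remaining.

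Case 3 requires compatible timing, so a new case 3 event in this window is unlikely for a completer, though a delayed effect is not excluded. A subject who terminates early can enter the window much closer to a dose, and there the rule matters more.

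**The case against.** The strongest reply is that the definitions are guidance for a clinical judgement and not an algorithm. The Investigator will make a determination, every assessed event will receive a category, and a blank is handled by the SAP. This stands, and it limits the effect: the problem is inconsistent or under-inclusive classification. A reader might infer that some events will go unclassified; the documents do not support that.

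A second reply is that the reasonable-possibility sentence directly follows the definitions and can be read as the overarching test, with the paired use of associated and related under Reporting being loose restatement. That reading is possible. It does not remove the problem, because RELATED still requires that no other cause can be identified.

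A third reply is that little depends on the category. This is largely right. The 24-hour notice covers "any SAE (regardless of whether the event is assessed as related or unrelated to study drug", and it also covers any AE that is potentially FDA-reportable. The Sponsor makes the final SUSAR determination. All AEs are collected from Day 1 dosing through EOT or ET and are listed, and the safety data have no inferential analysis. Follow-up of ongoing related AEs (Protocol 4.6 and 7.2.1) is worded as permitted, not required. What remains is the three uses of the category set out above.

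**Conclusion.** The point holds as a **minor** defect of definition. The two categories are not exhaustive, and RELATED excludes some events that meet the protocol's own reasonable-possibility standard. Confidence is high for the gap in the text. It is not high for any particular practical effect, because the documents do not allow the affected AEs to be counted.

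Two stronger conclusions might be inferred and should not be:

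- **That serious-event reporting is compromised.** SAE notification does not depend on relationship, and the SUSAR decision does not rest with the Investigator. Only the related element in the FDA-reportable definition is touched.
- **That completers will lose many events after discharge.** Their related-only period begins 168 hours after the last dose, so the concern there is mainly with early terminations.

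The all-TEAE tables, the AE listings and the PK analyses are unaffected. The verdict assumes that the 'and' in each definition means that both conditions must be met, which is its plain reading.

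**What to change.** Make the categories complementary in Appendix 1, using the standard that the protocol already contains:

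- **RELATED:** there is a reasonable possibility that the event was caused by study drug.
- **NOT RELATED:** there is no reasonable possibility that the event was caused by study drug.

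Remove the absence of any other identifiable cause as a condition for RELATED. Keep time course and other causes as factors for the Investigator to weigh. Every assessed event then falls into exactly one category, and the related and associated elements of the FDA-reportable definition rest on the same test. Making NOT RELATED the residual category would also close the gap, but it would keep the conflict with the reasonable-possibility sentence.

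The cost is a change to the appendix wording and an instruction to the site. The SAP tables need no change, since they take the Investigator's category as entered. The downside is that a few more events may be classed as related; the documents do not allow a count.

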Appendix 2: Clinical Laboratory Evaluations

a. Performed at Screening and Check-in (Day -1) only.

b. Performed at Screening only.

c. Performed at Screening, Check-in (Day -1), and End of Treatment (EOT)/Early Termination (ET) only.

Appendix 3: Total Blood Volume

The following blood volumes will be withdrawn for each subject participating in this study:

| Assessment | Approximate Blood Volume per Sample (mL) | Approximate Total Volume (mL) |
|--|--|-------------------------------------|
| Serology | CCI | |
| Hemoglobin A1c (HbA1c) | | |
| Primary pharmacokinetic (PK) sampling | | |
| Clinical laboratory tests: | | |
| Complete blood count (CBC) | | |
| Clinical chemistry panel | | |
| Coagulation parameters | | |
| Serum pregnancy test (female subjects | | |
| only) | | |
| Serum follicle-stimulating hormone (FSH; | | |
| post-menopausal female subjects only) | | |
| Thyroid-stimulating hormone (TSH) | | |
| | | |

If extra blood samples are required, the maximum blood volume to be withdrawn per subject will not exceed 400 mL.

Appendix 4: Schedule of Assessments

| | | | | | | | | - | | - | - | - | S | tudy | v Daj | ys | - | | | | | | | | | - | Clinic Discharge/ EOT (Day 25) or ET ^v | Follow -up Phone Call (EOS) |
|---|----------------------------------|----------------------|----|---|---|---|---|---|---|----|---|---|---|------|-------|----|----------------|----------------|----------------|----------------|----|---|---|---|---|---|---|---|
| Study Procedures ^a | Screening (Days -29 to -2) | Check-in (Day -1) | | 2 | 3 | 4 | 5 | 6 | 7 | 8 | 9 | | | | | | | | 17 | | 19 | | | | | | | 7 (±2) days post EOT or ET ^w |
| Confined to the CRU | | Х | Х | Χ | Х | Х | Х | Х | Х | Х | Х | Х | Х | Χ | Х | Х | Χ | Х | Х | Х | Х | Х | Х | Х | Х | Х | Х | |
| Inclusion/Exclusion Criteria | Х | Х | | | | | | | | | | | | | | | | | | | | | | | | | | |
| Informed Consent | Х | | | | | | | | | | | | | | | | | | | | | | | | | | | |
| Demographics | Х | | | | | | | | | | | | | | | | | | | | | | | | | | | |
| Medical History | Х | Хь | | | | | | | | | | | | | | | | | | | | | | | | | | |
| Height/Weight/BMI | Х | Xc | | | | | | | | | | | | | | | | | | | | | | | | | | |
| Physical Examination ^d | Х | Х | | | | | | | | | | | | | | | | | | | | | | | | | Х | |
| 12-lead ECG ^e | Х | Х | Х | | | Х | | | | Х | | | Х | | | | Х | | | Х | | | Х | | | | Х | |
| Vital Signs ^f | Xg | Xg | Х | Х | | Х | | | | Х | Х | | Х | | | | Х | | | Х | | | Х | | | | Xg | |
| HDYF? Inquiry ^h | Х | Х | Х | Х | Х | Х | Х | Х | Х | Х | Χ | Х | Х | Х | Х | Х | Х | Х | Х | Х | Х | Х | Х | Х | Х | Х | Х | Х |
| AEs/SAEs ⁱ | Х | Х | Х | Х | Х | Х | Х | Х | Х | Х | Х | Х | Х | Х | Х | Х | Χ | Х | Х | Х | Х | Х | Х | Х | Χ | Х | Х | Х |
| LOXO-305 Dosing | | | Xj | | | | | | | Xk | | | | | | | | | | X ^m | | | | | | | | |
| Omeprazole Dosing | | | | | | | | | | | | | | | | | X ¹ | X ¹ | X ¹ | X ^m | | | | | | | | |
| | | 1 | I | I | 1 | | | I | | I | I | I | I | | | I | 1 | I | I | | | | | 1 | I | 1 | | 1 |
| Clinical Laboratory Evaluations ^p | Х | Х | | | | х | | | X | | | | X | | | | | | X | | | | X | | | | Х | |
| Hepatitis and HIV Screen | Х | | | | | | | | | | | | | | | | | | | | | | | | | | | |
| HbA1c Test ^q | Х | | | | | | | | | | | | | | | | | | | | | | | | | | | |
| Drug Screen ^r | Х | Х | | | | | | | | | | | | | | | | | | | | | | | | | | |

Protocol Version 2.0, 29 January 2020

Protocol Covance Study: 8422329

| | | | | | | | | | | | | | S | tudy | v Daj | ys | | | | | | | | | | | Clinic Discharge/ EOT (Day 25) or ET ^v | Follow -up Phone Call (EOS) |
|--|----------------------------------|---|---|---|---|---|---|---|---|---|---|----|----|------|-------|----|----|----|----|----|----|----|----|----|----|----|---|---|
| Study Procedures ^a | Screening (Days -29 to -2) | | | 2 | 3 | 4 | 5 | 6 | 7 | 8 | 9 | 10 | 11 | 12 | 13 | 14 | 15 | 16 | 17 | 18 | 19 | 20 | 21 | 22 | 23 | 24 | | 7 (±2) days post EOT or ET ^w |
| Prior and Concomitant Medications ^s | X | Х | Х | X | Х | X | X | X | Х | Х | Х | X | Х | X | Х | X | X | X | X | X | X | Х | X | X | X | X | Х | Х |
| Serum Pregnancy Test ^t | Х | Х | | | | | | | | | | | | | | | | | | | | | | | | | Х | |
| FSH Test ^u TSH Test | X X | | | | | | | | | | | | | | | | | | | | | | | | | | | |

Abbreviations: AE = adverse event; BMI = body mass index; BP = blood pressure; CBC = complete blood count; CK = creatine kinase; CRU = Clinical Research Unit;

ECG = electrocardiogram; EOS = End of Study; EOT = End of Treatment; ET = Early Termination; FSH = follicle-stimulating hormone; HbA1c = hemoglobin A1c; HDYF? = How Do You Feel?; HIV = human immunodeficiency virus; ICF = Informed Consent Form; PK = pharmacokinetic; SAE = serious adverse event; TSH = thyroid-stimulating hormone; UA = urinalysis.a. For details on study procedures, see Section 7.

b. Interim medical history only.

c. Weight and BMI (based on Screening height) only.

d. A complete physical examination will be performed at Screening. An abbreviated physical examination will be performed at Check-in (Day -1) and at EOT (Day 25).

- e. 12-lead ECGs will be collected after the subject has rested in the supine position for at least 10 minutes, and will be obtained prior to and as close as possible to the scheduled blood draws at Screening and Day -1, Day 1 (predose and 2 hours after LOXO-305 dosing), Day 4 (ie, 72 hours after LOXO-305 dosing on Day 1), Day 8 (predose), Day 11 (ie, 72 hours after LOXO-305 dosing on Day 8), Day 15 (predose), Day 18 (predose), Day 21 (ie, 72 hours after LOXO-305 dosing on Day 18), and at EOT/Day 25 (168 hours after LOXO-305 dosing on Day 18) or ET.
- f. Vital signs measurements (supine BP and pulse rate) will be obtained at Screening and Day -1, Day 1 (predose and 2, 4, 8, and 12 hours after LOXO-305 dosing), Day 2 (ie 24 hours after LOXO-305 dosing on Day 1), Day 4 (ie, 72 hours after LOXO-305 dosing on Day 1), Day 8 (predose and 2, 4, 8, and 12 hours after LOXO-305 dosing [on Day 8]), Day 9 (ie 24 hours after LOXO-305 dosing on Day 8), Day 11 (ie, 72 hours after LOXO-305 dosing on Day 8), Day 15 (predose), Day 18 (predose and 2 hours after LOXO-305 dosing on Day 18), Day 21 (ie, 72 hours after LOXO-305 dosing on Day 18), Day 25 (168 hours after LOXO-305 dosing on Day 18) or ET. Vital signs measurements should be carried out prior to and as close as possible to having blood drawn. Blood pressure and pulse rate will be measured using the same arm for each reading after the subject has been supine for at least 5 minutes.

g. Oral temperature and respiratory rate will also be obtained at at Screening, Day -1, and at EOT/Day 25 (168 hours after LOXO-305 dosing on Day 18) or ET.

h. An HDYF? inquiry will be performed at Screening (after the ICF is signed), at Check-in (Day -1), at each postdose vital signs assessment, and at an appropriate time for all other days.

i. Adverse events and SAEs will be collected beginning at informed consent. Adverse events will be recorded throughout the study (ie, from signing of the ICF until EOS, or until ET if the subject discontinues from the study and does not complete a follow-up phone call), either as subject medical history (if the event is reported as beginning prior to signing of the ICF or if the event occurs prior to study drug administration on Day 1 and is assessed as not related to study procedures by the Investigator [or designee]) or as AEs (if the event occurs after signing of the

| Protocol | CONFIDENTIAL |
|------------------------|------------------------------------|
| Covance Study: 8422329 | Protocol Reference: LOXO-BTK-20014 |

ICF but prior to study drug administration on Day 1 and is assessed by the Investigator [or designee]) as related to study procedures, or if the event occurs after study drug administration on Day 1 through EOT or ET regardless of relationship to study drug). From EOT or ET through EOS, only AEs assessed as related to study drug are to be recorded. All SAEs that develop from the time of ICF signing until EOS (or ET if the subject discontinues from the study and does not complete a follow-up phone call) are to be reported.

- j. On Day 1, LOXO-305 will be administered in the morning, either following a fast of at least 10 hours prior to and 4 hours after the LOXO-305 dose or approximately 30 minutes after the start of a standard breakfast, according to the treatment sequence the subject is randomly assigned to. Standard breakfast should be entirely consumed within 30 minutes.
- k. On Day 8, LOXO-305 will be administered in the morning, either following a fast of at least 10 hours prior to and 4 hours after the LOXO-305 dose or approximately 30 minutes after the start of a standard breakfast, according to the treatment sequence the subject is randomly assigned to. Standard breakfast should be entirely consumed within 30 minutes.
- 1. On Days 15, 16, and 17 omeprazole will be administered in the morning following a fast of at least 8 hours prior to the omeprazole dose, followed by a standard breakfast administered approximately 1 hour after dosing. Standard breakfast should be entirely consumed within 30 minutes.
- m. On Day 18, LOXO-305 and omeprazole will be co-administered in the morning, following a fast of at least 10 hours prior to and 4 hours after the omeprazole and LOXO-305 coadministration.

CCI

- p. Clinical chemistry panel including CK (fasted at least 8 hours), coagulation parameters, CBC, and UA will be performed at Screening, Check-in (Day -1), Days 4, 7, 11, 17, 21, and at EOT (Day 25) or ET.
- q. Hemoglobin A1c test performed at Screening only.
- r. Alcohol breath test and drugs of abuse urine test, including cotinine. Results from the alcohol and drug tests will be used to determine subject eligibility per the inclusion/exclusion criteria.
- s. Prior and concomitant medication administration will be recorded beginning at informed consent. In addition, all Investigator-approved medications taken by a subject within 30 days prior to study drug administration for non-prescription medications, will be recorded on the subject's electronic Case Report Form.
- t. Female subjects only.
- u. Post-menopausal female subjects only.
- v. EOT is defined as when the subject is released from the CRU following completion of all assessments through Day 25. ET is defined as when the subject is released from the CRU if the subject terminates the study early. Vital signs, ECG, and safety laboratory results for clinical chemistry, hematology, coagulation, and UA are to be available for review by the Investigator or designee prior to subject release from the CRU at the EOT or ET visit.
- w. To be performed 7 days (± 2 days) following EOT or ET. EOS is defined as when the CRU contacts the subject by a follow-up phone call 7 days (± 2 days) after the EOT visit or ET visit to determine if any SAE or study drug-related AE has occurred since the EOT or ET visit. All subjects who received LOXO-305 (including subjects who are terminated early) will be contacted.

